9.0 SUBJECT DISCONTINUATION OF ACTIVE TREATMENT

Participants can choose to discontinue their participation in this study at any time for any reason.

10.0 CONCOMITANT MEDICATIONS

Use of concomitant treatments for both tobacco cessation and depression will be assessed at each time point. Individuals who report using self-report any other quit smoking treatment, including FDA-approved quit smoking medications (e.g., nicotine patch, nicotine gum, Zyban), during the screening phase will not be eligible to participate in the study. At the 2 and 6-month follow-up assessment, participants will be asked about their use of FDA-approved quit-smoking and pharmacotherapy for depression. Initiating use of FDA-approved quit-smoking medications during the study is allowed.

11.0 ADVERSE EVENTS

11.1 Adverse Events

This is a low-risk study with no intervention agent/drug. Because this is a smoking cessation intervention, some participants may quit smoking cigarettes and may experience the physical and psychological consequences of smoking abstinence, such as nicotine withdrawal symptoms. As part of the informed consent procedures, participants will be informed about potential nicotine withdrawal symptoms and effects of abstinence. The intervention provides strategies designed to cope more effectively with symptoms of nicotine withdrawal. Finally, participants will be given information on pharmacotherapy for smoking cessation (e.g., nicotine patch) and how to obtain these medications.

11.2 Collection and reporting of AEs and SAEs

Any adverse events detected during this study will be recorded in the Adverse Event Summary Form and reported as follows.

Monitoring.

Throughout the study, the project manager and outcome assessors will monitor participants' progress and responses to surveys for adverse events and protocol compliance. The study manager will complete quarterly reports on participant progress and status, any adverse events, and any protocol deviations.

Reporting.

All study staff working on the trial will be trained and required to report all unexpected and adverse events to the project manager and the Principal Investigator. A form will be available for this purpose. Adverse events beyond what would be expected in the course of smoking cessation will be reported to the Fred Hutch's IRB in accordance with Fred Hutch policy.

Reporting SAEs. For AEs meeting the criteria for an SAE, regardless of attribution, the study coordinator will inform the Fred Hutch IRB per their reporting guidelines and will complete and submit a NIDA SAE report form within 72 hours of the reported event. Should additional information become available after the initial report, a revised report will be submitted as soon as possible.

Reporting AEs that do not meet the criteria for SAE. All reported AEs will be collected and reported via the study's electronic database. AEs that are expected will be summarized at the time of continuation review.

Reporting UEs that do not meet the criteria for AEs. The study team will report any UEs to the Fred Hutch IRB per their reporting guidelines. Fred Hutch will report the UE to the sponsor in accordance with the protocol.

Definitions

In general, unexpected events (UEs) include any event, adverse or otherwise, that was not described as part of the study risks. For this trial, an example of an unexpected event that is not adverse is a participant who has become very unhappy with trial procedures. Adverse events (AEs) are any untoward occurrence with a trial participant whether or not it can be considered to be related to their smoking cessation intervention. Examples of adverse events in this trial could include development or worsening of depression symptoms. Serious adverse events (SAEs) include any AE that results in death, a real risk of dying, inpatient hospitalization, persistent or significant disability/incapacity, or AEs that require intervention to prevent permanent impairment or damage. In this trial, an example of a serious adverse event would be a suicide attempt.

Management of SAEs or other study risks

UEs, AEs, and SAEs will be reported to the Principal Investigator as soon as staff members are aware of them. If there is any doubt as to whether an event qualifies as a UE, AE, or SAE, staff members will be trained and encouraged to err on the side of caution – and to bring the event to the Principal Investigator's attention for review. The PI will be responsible for managing UEs, AEs, and SAEs.

Attribution

The Principal Investigator will decide if a UE should be classified as an AE. If an event is classified as an AE, further attribution will be determined, as follows:

- Related – AEs that are definitely, probably, or possibly related to the intervention.
- Not Related – AEs that are doubtfully related or clearly not related to the intervention.

12.0 DATA AND SAFETY MONITORING PLAN

This study is a low-risk, single-site, randomized 2-arm pilot trial of a behavioral intervention for smoking cessation, monitoring of participant safety and data quality will be overseen by the PI, who will have weekly meetings with the study team to discuss study progress, including recruitment and retention, adverse events, and protocol adherence. Detailed DSMP is included in Appendix A.

13.0 DATA MANAGEMENT/CONFIDENTIALITY

The investigator will ensure that data collected conform to all established guidelines. Each subject is assigned a unique subject number to protect subject confidentiality. Only Fred Hutch IRB-approved project staff will have access to study data. All data will be maintained on a secure-access drive in permission-restricted folders only accessible to project staff. All workstations and servers are physically secured in locked offices, reside behind the Fred Hutch firewall, and fully participate in Windows NT security. The data study folder will be further safe-guarded against unauthorized access by network user login authentication controls.

In no case will patient identifiers or data be provided to any person or entity outside the IRB-approved project team. Protected health information will not be disclosed, copied, transmitted by email, or transmitted in total or in part to anyone not connected with the approved protocol and not approved by the Fred Hutch IRB. We will limit our acquisition of identifiable information to the minimum amount of information necessary to link subject data, obtain contact information for recruitment of subjects, and collect pertinent data necessary to complete the study aims.

Any data included in manuscripts or publications stemming from this study will be presented as aggregate data only, and in a way that no individual could be identified. At the end of the study, after all manuscripts are published, all identifiable files and crosswalks will be destroyed in accordance with Fred

Hutch IRB policy (7 years after the end of the study). Electronic media used to store all data will be cleaned or destroyed so the data is not retrievable. As a result of these measures, we do not expect any invasion of privacy or breach of confidentiality.

When any study personnel are no longer a part of the research team, the PI will remove that person's access to all study data and notify the Fred Hutch Information Security Officer of such action.

Online Surveys. The study database will be designed and maintained by Datatope, kept behind FHCRC firewall. Only key study staff will have access to the study database system. All staff have received Human Subject Research and HIPAA training. All data will be stored in a secure password protected computer folder, which only authorized research staff will have access to.

Mailed Surveys. Numerous safeguards will keep hard copy data secure. All hard copy data will be kept in a locked file cabinet accessible only by authorized research staff.

Actify and QuitGuide app-based Intervention. Numerous safeguards will keep electronic data secure. A secure password is required to access computers at our site, and computer networks are on secured servers that meet or exceed federal confidentiality standards. Each participant will have access to their website protected with a login. All connections to this website will be made using the secure sockets layer (SSL). Participant data are maintained on a server in a locked server room at Fred Hutch. Full access to the server is restricted to two staff members of the Fred Hutch Public Health Sciences Information Technology (PHS-IT) group and the two staff members of Datatope Inc. Participants access their intervention app by providing login credentials on the app, which is hosted on a secure server. The Login server has no access to the study database. It can send login credentials and, upon successful login, it can receive the participant's responses provided in the intervention app to questions related to smoking and values. No potentially identifying information is entered into the app by the participant. All communication with the Actify and the QuitGuide app occurs over Secure Sockets Layer (SSL). The intervention app stores participant usage data. The only participant identifier that will be transmitted to this database server will be their login id. The site only stores data related to site usage.

14.0 STATISTICAL CONSIDERATIONS

14.1 Study Design

Randomized controlled 2-arm pilot trial

14.2 Primary/Secondary Endpoints/Hypotheses and Analytical Methods

Data analyses will be conducted using the intent-to-treat approach, except where otherwise indicated.

Aim 1. Conduct a pilot, randomized controlled trial (n=240) to test the primary outcome of treatment acceptability and secondary outcomes of efficacy and mechanism of change for the two treatment groups: Actify vs. QuitGuide.

ENDPOINTS

- The primary acceptability endpoints are number of app openings and overall satisfaction ratings.

- For smoking cessation:
 - The primary endpoint is the 30-day point prevalence abstinence (PPA) at 8 weeks post-randomization, which is comparable to the primary endpoints of the two extant trials of smartphone apps for smoking cessation [10, 34].
 - The secondary endpoints are 7- and 30-day PPA at 6 months, 7-day PPA at 8 weeks, and biochemically-confirmed abstinence from any nicotine/tobacco product (other than FDA-approved cessation medications) between baseline and 8-week and 6-month follow-ups.
- For mechanism of change,
 - The primary endpoint is the change in BADS scores between baseline and the 8-week follow-up
 - The secondary endpoint is the change in depressive symptoms over the same time period.

ANALYTICAL METHODS

Linear regression will be used to evaluate treatment effects between the two arms for continuous endpoints. This model will adjust for any demographic or other variables that differ between study arms at baseline and are related to outcome as well as the stratification factors (depression severity, sex assigned at birth, and level of smoking). To compare binary endpoints between two arms (e.g. smoking abstinence), a logistic regression model will be conducted with control for potential confounding variables and the stratification variable. Sensitivity analyses excluding participants using concomitant treatment for smoking cessation and/or depression will also be conducted.

Additional exploratory analyses will be conducted. To explore differential treatment effects by pre-quit depression, we will preliminarily test the interaction of treatment group assignment and pre-quit depression and present descriptive data on quit rates for the four subgroups (Actify, depressed; Actify non-depressed; QuitGuide, depressed; QuitGuide non-depressed). To evaluate the theory underlying BAT-D for smoking cessation, we will examine change in BADS scores between baseline and 8-week follow-up as a predictor of 30-day PPA at 6-month follow-up using a logistic regression model. To generate empirical evidence to set usage benchmarks for the Actify app, we will evaluate the relationship between app “dosage” and cessation outcomes by regressing 30-day PPA at 8 weeks on objective measures of app utilization (e.g., number of app logins, total duration of use) using logistic regression. Similar to our feature analysis of SmartQuit that guided future app development [69], we will also regress 30-day PPA at 8 weeks on utilization of specific app components (e.g., scheduling, mood tracking) to determine “active ingredients.” To evaluate the relationship between user characteristics and treatment utilization and outcomes, we will use logistic (for cessation outcomes) or negative binomial (for login count data) models and baseline data as predictors. To examine sex as a biological variable, we will preliminarily test for sex differences in treatment response by descriptively examining results separately by sex.

Missing data: Consistent with prevailing standards for smoking cessation trials [88], participants with missing smoking data will be considered non-abstinent in the primary analysis. As a sensitivity analysis, we will also report abstinence rates from complete case analyses and multiple imputation. Treatment acceptability and mechanism of change (i.e., behavioral activation [BADS] and depression [PHQ-8] scores) will be analyzed using complete case analysis.

Modified intent-to-treat approach. Because treatment acceptability is the primary outcome of this pilot trial, and because a valid assessment of acceptability is not possible in cases where there is pre-intervention attrition (i.e., never downloading or opening the assigned app), we will use a modified intent-to-treat approach in which only those participants who open their assigned app at least once will be included in the outcome analyses.

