Collectively, these results demonstrate (1) our ability to recruit and retain participants, (2) high engagement with the app, and (3) a promising signal for impact on theory-based change processes and cessation outcomes, which were descriptively higher for Actify than for our ACT SmartQuit app among the subgroup of depressed smokers (31% vs. 23% for complete-case 7-day PPA and 19% vs. 6% for 30-day PPA at short-term follow-up) and better than published quit rates of 7% for SmokefreeTXT alone [60]. Engagement was also higher for Actify than SmartQuit (average of 20 logins over 6 weeks for Actify vs. 12 logins over 2 months for SmartQuit). Preliminary quit rates also compare favorably to the previous trial of face-to-face BAT-D for depressed smokers (i.e., CO-confirmed, 7-day PPA rate of 17% at end of treatment vs. 31% for Actify) conducted by our consultant, [name] [52]. These promising findings warrant completing development of the Actify app, modifying it to improve usability, and evaluating the complete product in a controlled pilot trial.

2.2.2. Next steps.

Following our extensive development work to translate BAT-D into an engaging mHealth app format, the next step is to complete the development of Actify by incorporating the smoking cessation content into the established structure of the app. After completion of this next stage of work, the fully developed Actify app will be ready for pilot randomized trial to obtain a preliminary estimate of its acceptability, efficacy, and effects on behavioral activation and depressive symptoms as the theory-based mechanisms of change for smoking cessation (see Figure 1 for development timeline). This plan is consistent with Stage Ia and Ib of the NIDA Behavioral Therapies Development Model [61] and with the aims of the NIDA R34 mechanism to support behavioral and integrative treatment development.

Figure 1. Progress to date toward development of a complete version of the Actify app and launch of a pilot trial.

2.2.3. Preliminary studies of mHealth apps for smoking cessation.

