8.0 SUBJECT EVALUATION

8.1 Data Collection Overview

Table 1. Phase II Pilot Study Data Collection Overview

Measure	Screening	Baseline	8-week follow-up	6-month follow-up	Purpose
PHQ-8 (8 items)	X	X	X	X	Eligibility, mechanism of change
Other eligibility criteria (~11 items)	X				Eligibility
Demographics (~10 items)		X			Sample Description
FTND (6 items)		X			Sample Description
Treatment satisfaction (~8 items)			X		Acceptability
Treatment preferences (~5 items)		X			
Tobacco/Nicotine use (~12 items)		X	X	X	Efficacy
Behavioral Activation for Depression Scale (25 items)		X	X	X	Mechanism of change
Concomitant treatment (2 items)	X	X	X	X	Stratification, sensitivity analysis
Total number of items	36 items	70 items	53 items	45 items	
Estimated duration	~5-8 min	~10-15 min	~15-20min	~10-15 min	

8.2 Enrollment Procedures.

The study recruitment website provides basic information about the study, FAQ, information about the study team and Fred Hutchinson Cancer Research Center (FHCRC), and a portal to the informed consent form, screening, and baseline surveys.

We will use the identical enrollment method proven successful in our previous, remotely-conducted RCTs. Specifically, for participants who screen eligible on the recruitment website and provide their email address, we will instantly send them an email (and two reminders over a 14-day period) inviting them to complete a secured online survey to provide informed consent and complete the baseline assessment. Those not consenting and completing the online enrollment process within 14 days will be sent an email notifying them that they were not enrolled and provide both the QuitGuide app and the 800-QUIT-NOW phone number to reach their state's quitline.

To address potential fraudulent responses to web-based screening surveys, we will use the same methods used in our previous studies: CAPTCHA verification, ineligibility if the IP address was previously used or suspicious, and telephone contact by research staff if any aspect of automated data collection revealed suspicious activity (e.g., very brief survey completion times or unusual patterns in email addresses). To further deter fraudulent attempts to enter the study, no compensation will be provided for completion of the screening and baseline surveys.

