14.3 Sample Size and Power

As a pilot treatment development project, this study is not powered to detect statistically significant differences by treatment group. However, we plan to compare the outcomes of the two interventions to obtain a preliminary estimate of effect size. We will use these pilot data to optimize the treatment and study design and to prepare for a rigorous test of the efficacy of Actify in a subsequent R01. We plan to accrue a total of 240 patients in the pilot RCT for a balanced design. The NIDA Stage Model of behavioral treatment development suggests that pilot treatment development trials should include approximately 15-30 participants per arm to test feasibility [61]. However, as demonstrated in a recent simulation focused on sample size for pilot studies [87], binary outcomes (e.g., smoking abstinence) require higher sample sizes for reasonable precision of the effect size estimate than do continuous outcomes. To be conservative, and in consideration of the higher recruitment capacity in remotely conducted studies involving standalone mHealth interventions, we chose to include 60 subjects per arm within each stratum (depressed vs. non-depressed), as a sample size of 60 is a point of diminishing returns in terms of precision of effect size estimates for binary outcomes [87]. Thus, each arm will have 120 participants, of which 60 will meet criteria for mild to moderate depression.

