14.4 Randomization

Following completion of the baseline survey, the web-based program will randomize participants to receive either Actify or QuitGuide with a 1:1 allocation ratio. The randomization algorithm will be developed by the study biostatistician, with stratification by presence of mild to moderate depressive symptoms (PHQ-8 < 5 or PHQ-8 ≥ 5), sex assigned at birth (2 levels: male or female) and level of smoking (2 levels: 20 or more cigarettes per day vs. < 20). Randomized participants will be emailed a secured link to download their assigned app. All participants will be emailed identical once-weekly reminders to use their assigned intervention. Although we project, based on recent data from our trial of web-based interventions [8], that the vast majority (92%) of outcome assessments will be completed via web-based survey, any outcome evaluator who has direct contact with participants will be blinded to treatment group assignment.

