7.2 Plans for final analysis

Data analyses will be conducted using the intent-to-treat approach, except where otherwise indicated. Analyses will consist of a comparison between two arms on three outcomes: acceptability, efficacy for smoking cessation, and effect on BAT-D theory-based mechanisms of change. The primary acceptability outcomes are number of app openings and overall satisfaction ratings. For smoking cessation, the primary endpoint is self-reported 30-day point prevalence abstinence (PPA) at 8 weeks post-randomization, which is comparable to the primary endpoints of the two extant trials of smartphone apps for smoking cessation [10, 34]. The secondary endpoints are self-reported and biochemically confirmed 7- and 30-day PPA at 6 months, 7-day PPA at 8 weeks, and biochemically-confirmed abstinence from any nicotine/tobacco product (other than FDA-approved cessation medications) between baseline and 8-week and 6-month follow-ups. For mechanism of change, the primary endpoint is the change in BADS scores between baseline and the 8-week follow-up and the secondary endpoint is the change in depressive symptoms over the same time period.

Linear regression will be used to evaluate treatment effects between the two arms for continuous endpoints (e.g. treatment satisfaction ratings). This model will adjust for any demographic or other variables that differ between study arms at baseline and are related to outcome as well as the stratification factors (depression severity, sex assigned at birth, and heaviness of smoking). To compare binary endpoints between two arms (e.g. smoking abstinence), a logistic regression model will be conducted with control for potential confounding variables and the stratification variable. Sensitivity analyses excluding participants using concomitant treatment for smoking cessation and/or depression will also be conducted.

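### Baseline BADS is not a fixed covariate in the analysis of change in BADS, so the interval for this secondary estimate is likely wider than it need be

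*Combined protocol and SAP*

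**What the plan says.** Section 14.2 defines the mechanism endpoint: "The primary endpoint is the change in BADS scores between baseline and the 8-week follow-up". Section 7.2 of the DSMP (Appendix A) repeats it. Continuous endpoints are analysed by linear regression. On covariates, 14.2 states: "This model will adjust for any demographic or other variables that differ between study arms at baseline and are related to outcome", in addition to the stratification factors (depression, sex at birth, smoking level). DSMP 7.2 gives the same rule. Neither section names baseline BADS, sets a threshold for a difference between arms, or says how a relation to outcome is judged.

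Table 1 in section 8.1 schedules the 25-item BADS at baseline, 8 weeks and 6 months, so the baseline score is available. The depression factor comes from a different instrument: section 14.4 describes randomization "with stratification by presence of mild to moderate depressive symptoms", as a two-level PHQ-8 split at 5.

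On purpose, section 2.2.2 says the pilot is run "to obtain a preliminary estimate of its acceptability, efficacy, and effects on behavioral activation and depressive symptoms as the theory-based mechanisms of change", and section 14.3 says "we plan to compare the outcomes of the two interventions to obtain a preliminary estimate of effect size". BADS is analysed on complete cases, and under the modified intent-to-treat rule in 14.2 "only those participants who open their assigned app at least once will be included in the outcome analyses".

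**The concern.** The baseline value of an outcome is usually among its strongest predictors. A change-score model without it fixes the baseline slope at 1; regression estimates the slope and leaves less residual variance unless 1 happens to be right. Choosing covariates by observed imbalance does not solve this, because it responds to chance differences between arms rather than to prognostic value. In a 1:1 stratified trial the rule will often leave baseline BADS out.

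Two things are at stake. The interval for the BADS effect may be wider than the collected data allow, in a study whose stated aim is estimation. And because the two conditions are undefined, two statisticians could fit different models to the same data.

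**Working it through.** **The plan's own figure.** 60 per arm per depression stratum × 2 strata × 2 arms = 240, as stated in 14.3. No precision figure is given for BADS, so there is none to reproduce.

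**Inputs from the documents.** SD of BADS change 32 (section 2.2.1.d: 16 completers, 6 weeks). Retention 89% (section 7.4), so 0.89 × 120 ≈ 107 per arm.

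**Assumed inputs, not in the documents.** r, the baseline-to-8-week BADS correlation: 0.3, 0.5, 0.7. c, the size of the BADS–PHQ correlation: 0.5 to 0.7. k, the 8-week SD divided by the baseline SD: 0.8 to 1.3. A k above 1 is plausible because PHQ-8 is capped at 19 at entry but not at 8 weeks.

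**Always versus never including baseline BADS, PHQ-8 stratum already in the model.** Take the stratum as a 50/50 split of a normal score, with PHQ linked to 8-week BADS only through baseline BADS. Then

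SE ratio = √{ k²(1−r²) / [k²(1−r²) + (1−kr)²(1−2c²/π)] }.

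- k=1, r=0.3, c=0.5: 0.91/(0.91 + 0.49×0.841) = 0.688; root 0.830; cut 17.0%.
- k=1.2, r=0.5, c=0.5: 1.08/(1.08 + 0.16×0.841) = 0.889; root 0.943; cut 5.7%.

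Cut in SE, over c = 0.5–0.7:

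| k | r=0.3 | r=0.5 | r=0.7 |
|---|---|---|---|
| 0.8 | 23–26% | 19–22% | 16–18% |
| 1.0 | 15–17% | 10–12% | 6–7% |
| 1.2 | 9–11% | 5–6% | 1.2–1.4% |
| 1.3 | 7–9% | 3–4% | 0.3–0.4% |

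The gain vanishes when kr = 1. At k=1, r=0.5 an 11% cut is worth 1/0.89² ≈ 1.26, or about 26% more participants.

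**In BADS points (illustrative).** The 95% half-width without baseline BADS is 1.96 × 32 × √(2/107) = 8.57, treating 32 as a within-stratum SD. With equal SDs it falls to between 8.57×0.830 = 7.1 and 8.57×0.944 = 8.1. If 80% open the app (assumed), 0.80 × 0.89 × 120 ≈ 85 per arm; the half-width is 9.62 and falls to 8.0–9.1.

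**The rule as written.** It lies between never and always. I simulated 3,000 to 5,000 trials per setting, 107 per arm, balanced within the PHQ stratum; sex and smoking strata were not modelled. Three assumed readings of *differ* were tried. Excess over always adjusting, equal SDs, as true SD of the estimate / reported SE:

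| Reading | Baseline BADS enters | r=0.3 | r=0.5 | r=0.7 |
|---|---|---|---|---|
| p<0.05 | 2–4% of trials | 14–17% / 17–20% | 9% / 10–12% | not tabulated |
| p<0.20 | 12–17% | 9% / 15–17% | 4–5% / 9–11% | 3% / 5–6% |
| standardised difference >0.1 | 37–43% | 2–3% / 10–12% | 1.3–1.5% / 7% | 0.7–1.0% / 4% |

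The true loss is smaller than the reported one because the rule adjusts in the trials where imbalance is largest. Under the standardised-difference reading, also requiring a relation to change at p<0.05 altered entry materially only where the gain is already near zero.

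**The case against.** The plan is not a never-adjust plan. Its conditional rule can admit baseline BADS, and the depression stratum already recovers part of the gain. Under the loosest reading the true loss is only 1–3% with equal SDs, though the reported interval is still 4–12% wider. This stands, and it is why the always-versus-never figures are an upper guide.

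r, c and k are all assumptions. At r=0.8 with equal SDs the cut is 3.6–4.4%, at r=0.9 about 2%, and at r=0.8 with k=1.2 about 0.1%, so the 0.3% in the table is not a floor. If PHQ-8 entered as a continuous score, the equal-SD cuts would be 11–16%, 8–11% and 4–6%. These points widen the uncertainty without reversing the direction.

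The point widths depend on what the pilot SD represents. If 32 is an SD before stratum adjustment, the planned model gives about 8.1–8.5 and the adjusted one 6.9–7.9. The percentages are unaffected.

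The complete-case and app-opener restrictions can themselves bias the comparison. That is true, but it is separate from the choice of covariates.

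Finally, the study is not powered for group differences, mechanism of change is a secondary outcome, the precision argument in 14.3 concerns binary outcomes, and nothing says the BADS estimate will size the next trial. All of this limits the consequence.

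**Conclusion.** The point holds, as an optional improvement and not a validity defect. Baseline BADS is collected but not fixed in the model, and its entry depends on undefined conditions judged after the data are seen. With equal visit SDs and a BADS–PHQ correlation of 0.6, the excess over always adjusting runs from about 16% (true) and 18% (reported) under a p<0.05 reading at r=0.3, to about 1% and 4% under a standardised-difference reading at r=0.7. It is essentially nil if the 8-week SD is 1.3 times baseline and r is 0.7. Confidence in the direction is good; confidence in the size is limited, because the documents supply none of r, c or k. In no tabulated setting does always adjusting widen the expected interval, apart from the cost of one degree of freedom.

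**What to change.** In section 14.2 and DSMP 7.2, state that 8-week BADS (or its change) is regressed on arm, continuous baseline BADS and the three stratification factors, all included whatever imbalance is observed. With baseline in the model the arm coefficient is the same for either form of the outcome, so the endpoint need not change. The cost is one sentence in each place and one degree of freedom, with no new data.

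The same form may be used for PHQ-8 for consistency. Its stratum already gives coarse baseline adjustment, so the added gain there is small: about 2–8.5% with equal SDs for r from 0.8 down to 0.3. The undefined covariate rule would still apply to other continuous endpoints such as satisfaction; this change does not address that.
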